3.0 STUDY POPULATION

3.1 SELECTION OF THE STUDY POPULATION

The study will accrue patients with sessile appearing bladder masses who are felt by the treating physician to harbor MIBC.

Prior to TURBT at Cedars-Sinai, **ALL** subjects will undergo axial imaging for clinical staging in the form of contrast enhanced MRI of the abdomen and pelvis (standard of care). The pelvic MRI will be multiparametric (mp)-4D MRI incorporating high resolution diffusion weighted imaging (HR-DWI). Both the abdominal and pelvic MRI will have an official interpretation by a radiologist, thus both can be used in the care of the subject. Next, **ALL** subjects will undergo TURBT at which time, voided urine, blood and fresh frozen bladder tumor will be collected.

Many subjects present to Cedars-Sinai after their transurethral resection of bladder tumor (TURBT) at an outside facility and a repeat TURBT is not planned at Cedars-Sinai. Such subjects will undergo axial imaging for clinical staging in the form of contrast enhanced MRI of the abdomen and pelvis (standard of care). The pelvic MRI will be multiparametric (mp)-4D MRI incorporating high resolution diffusion weighted imaging (HR-DWI). Both the abdominal and pelvic MRI will have an official interpretation by a radiologist, thus both can be used in the care of the subject. Next, **ALL** subjects will have their outside TURBT formalin fixed paraffin embedded (FFPE) requested, specifically 1 H&E slide and 10 unstained slides.

Subsequently, those patients deemed to have muscle invasive, yet localized disease and are considered candidates for radical cystectomy by their treating physicians will proceed to radical cystectomy at which time another voided urine, blood and fresh frozen bladder tumor will be collected. Pathologic stage will be determined and reported on both the TURBT specimen and radical cystectomy specimen. Finally, subjects will be followed for 2 years to elicit outcome data.

Inevitably, a portion of subjects with bladder masses who are suspected of harboring BCa will not have bladder cancer (10%), BCa diagnosed may not be MIBC (20%) and some subjects may not desire radical cystectomy for their MIBC (20%), thus we anticipate the need to enroll and image 20 subjects to get to our final study population of 10 MIBC who have undergone mp-4D MRI, TURBT and subsequent radical cystectomy.

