11.0 STATISTICAL CONSIDERATIONS

11.1 STUDY OUTCOME MEASURES

We have previously performed RNA-seq on 25 MIBCs, to identify 3 key bladder tumor cell populations that are differentially represented across tumors. These cells show major molecular differences and their proportions within a tumor are strong predictors of the aggressiveness of the disease, as measured by time to recurrence. Further, we have applied this data to develop a deconvolution algorithm that is able to predict their proportions in other tumors within TCGA based on bulk RNA-seq data. Now, we will apply this deconvolution algorithm to the RNA-seq data from 10 tumors in conjunction with imaging data to search for image and genomic parameters that predict tumor stage, outcomes and the presence of each of the cancer cell types, as well as fibroblasts and different immune infiltrates.

Querying a small population for numerous parameters can lead to high false positive rates, thus from our retrospective work, we will apply 30 radiomics parameters and no more than 40 genes in our network analyses, prioritization of genes and their interactions will be done using Lynx, PINTA and String algorithms to perform annotation, clustering, enrichment analysis, and prediction of high-confidence triggers and mediators in various cell populations of interest. Predictions of gene interactions and reconstruction of molecular pathways for the phenotypes of interest will be done using PINTA and STRING algorithms. These pipelines will be executed at scale using cloud resources. In addition to cloud resources, we will leverage the existing infrastructure available to the [name] lab. The results will be annotated with information from Lynx knowledge base integrating > 35 biological databases and publicly presented for revision and analysis via Web-based user interface developed in the course of the project. Biostatistical and bioinformatic comparisons of the molecular profiles with MRI imaging characteristics will be performed using a variety of publicly available and locally developed software applications.

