11.2 SAMPLE SIZE CONSIDERATIONS

The main hypothesis to be tested is whether there is association between radiogenomic features and pathologic stage. The prospective study is a pilot study to: a) generate high quality data and b) show feasibility, which we will define as know-how to create a radiogenomic workflow and to learn about the correlation structure of the radiogenomics parameters of interest, which will allow us to design future studies with adequate power. Pearson's Correlation hypothesis tests with 5% significance level (two-sided) and 80% power allows sample sizes of 10 patients to detect a difference between the null hypothesis correlation of zero and the alternative hypothesis correlation of 0.76 (23). In addition, sensitivity and specificity of several potential predictors will be estimated. The maximum width of the 95% confidence interval for proportions (sensitivities or specificities) associated with sample sizes of 10 patients are 0.63 (24). We anticipate 50% of subjects presumed to have MIBC at the time of TURBT and/or presumed not to have metastatic disease to not complete the study, i.e., undergo radical cystectomy, which will denote true pathologic stage. Thus, our final sample size to enroll is 20.

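### Radiomic-gene links among 30 × 40 parameters in 10 patients have no chance benchmark beyond a cap on the number of parameters, and the raw joint correlation matrix cannot support the design of the next study

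*Combined protocol and SAP*

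**What the plan says.** Section 2.0 makes the correlation structure between radiomic and genomic parameters part of the feasibility objective. Section 11.2 repeats the aim, "to learn about the correlation structure of the radiogenomics parameters of interest", and gives its use: planning later studies of adequate power.

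Section 11.1 sets out the analysis. The sample is small: "we will apply this deconvolution algorithm to the RNA-seq data from 10 tumors in conjunction with imaging data". Section 3.1 gives the same number: "our final study population of 10 MIBC who have undergone mp-4D MRI, TURBT and subsequent radical cystectomy". The risk of chance findings is acknowledged and answered by a limit on parameters: "Querying a small population for numerous parameters can lead to high false positive rates, thus from our retrospective work", followed by "we will apply 30 radiomics parameters and no more than 40 genes in our network analyses". Gene prioritisation and gene interactions are assigned to Lynx, PINTA and STRING.

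The only significance level in the document is in section 11.2, where two-sided 5% Pearson tests with 10 patients are said to give 80% power at a correlation of 0.76. No section states a rule for calling a radiomic-gene link, an adjustment for the number of pairs, a regularised estimator, or a comparison with what chance alone would produce.

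**The concern.** A cap of 70 parameters is still seven times the number of patients. It leaves 30 × 40 = 1,200 radiomic-gene pairs, the pairs that the objective is about. Without a chance benchmark, the investigators cannot tell whether the links they find exceed what unrelated MRIs and RNA profiles would give.

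The matrix as a whole has a separate weakness. Ten patients cannot determine a 70-variable correlation matrix, and some summaries of it are fixed largely by the sample size. If the next study takes its effective number of tests, or a simulation model, from this matrix, it inherits figures that say more about the sample of 10 than about bladder cancer.

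**Working it through.** **Inputs.** 30 radiomic parameters, at most 40 genes and 10 tumors (section 11.1); two-sided 5%, 80% power and correlation 0.76 (section 11.2). Within-block correlation is not given, so I take 0 and 0.5 as a range.

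**1. The plan's own figure.** At n = 10 the two-sided 5% critical value is |r| = t/√(n − 2 + t²) with t = 2.306, so 2.306/√(8 + 5.318) = 0.632. The exact distribution of the sample correlation then gives 79.8% power at 0.76. The stated 80% is reproduced, for one pair.

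**2. Rank.** Centring 10 patients leaves n − 1 = 9 dimensions. At least 70 − 9 = 61 of the 70 eigenvalues are therefore zero, whatever the biology. The nine or fewer non-zero ones share all the variance, so the first takes at least 1/9 = 11.1%. In simulated independent noise it averages 17.6%; the true share is 1/70 = 1.4%. This uses no link threshold.

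**3. Effective number of parameters.** One standard measure is p²/Σr², summed over the whole matrix. For independent variables the truth is 70²/70 = 70. In a sample of 10, each off-diagonal r² averages 1/(n − 1) = 1/9, so the sum is about 70 + 70 × 69/9 = 606.7 and the measure is about 4,900/606.7 = 8.1. Now take an illustrative truth of seven blocks of 10 variables with correlation 0.5. The true value is 4,900/(70 + 70 × 9 × 0.25) = 4,900/227.5 = 21.5, while simulated samples of 10 give 6.8. The raw matrix returns roughly the same small number in both cases.

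**4. Chance links at the 5% level.** The expected count is 1,200 × 0.05 = 60. Simulation of unrelated blocks agrees (59.8), and the largest noise |r| among the 1,200 pairs averages about 0.89.

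**5. Spread of that count.** With independent features its SD is √(1,200 × 0.05 × 0.95) = 7.5, so about 90% of counts fall in 60 ± 1.645 × 7.5, or 48 to 72. With correlation 0.5 inside each block and none between blocks, the mean stays near 60 but the simulated 5th to 95th percentile range is about 16 to 146. These limits are simulation estimates and move by several links between runs.

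**6. Why not simply adjust each test.** Bonferroni over 1,200 pairs needs |r| > 0.943. Power at 0.76 then falls from 80% to 2.7%.

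**7. Precision of one pair.** The Fisher-z 95% interval is tanh(atanh r ± 1.96/√7). For an observed 0.5 this is tanh(0.549 ± 0.741), or −0.19 to 0.86.

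**The case against.** The strongest reply is that this is a pilot. Feasibility is defined as workflow know-how and learning about correlations; no full-rank matrix is promised, and pairwise estimates with intervals can inform a later study without inverting anything. That stands, and it is why the fix asks for exactly those intervals. It does not supply a chance benchmark for a named deliverable.

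Second, the 5% level belongs to a sample-size statement for a single correlation, and the plan never says links are drawn at p < 0.05. This also stands: the count of 60 is conditional on that level. The absence of any other rule is part of the gap, and the rank and first-component results do not depend on it.

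Third, Lynx, PINTA and STRING bring outside knowledge to the gene side. True, but nothing described for them addresses radiomic-gene correlations.

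Two stronger readings are tempting, and the documents support neither.

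- A reader might infer that 10 patients make a network of pure noise look connected. At a 5% cut-off, mean degree is 69 × 0.05 = 3.45 at any sample size, and simulation with 1,000 patients gives the same connected share (about 0.96) and top hub (about 8 links) as with 10. Those features reflect an unadjusted cut-off, not n = 10. At |r| > 0.76, only about 7 of 70 nodes join.
- A reader might infer that useful data lie idle, since section 11.1 reports "We have previously performed RNA-seq on 25 MIBCs". Those tumors are already used: "we have applied this data to develop a deconvolution algorithm". No MRI is mentioned for them, so they cannot help any of the 1,200 radiomic-gene pairs. They could inform only the 40 × 39/2 = 780 gene-gene pairs, and section 11.1 does not say whether their RNA-seq was bulk or single-cell.

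**Conclusion.** The point holds in a limited form and is a worthwhile improvement, not a defect that stops the pilot. Two parts need no assumption about how links are called: the 70-variable matrix has rank at most 9, and the cap leaves 1,200 radiomic-gene pairs with no planned comparison against chance.

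The size of the chance problem is conditional. About 60 false links are expected if the 5% level of section 11.2 is applied pair by pair. Their realised number could lie anywhere from about 16 to 146 if features correlate at 0.5 within blocks, against about 48 to 72 if they are independent. The true within-block correlation is unknown, and the simulations assume normal data. A single correlation at or above the powered value of 0.76 is therefore not evidence of a radiomic-genomic link when it is picked from 1,200.

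**What to change.** In section 11.1:

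1. Re-pair MRIs and RNA profiles at random across patients, which keeps each block's own correlations and breaks only the link between them. There are 10! = 3,628,800 pairings, so a large random sample of them is easy to draw. Compare the observed number and size of radiomic-gene links with this distribution, using a link rule fixed beforehand.
2. Name one global radiomic-genomic association statistic in advance and test it the same way.
3. Report pairwise correlations with 95% intervals.
4. State that the raw rank-9 matrix will not be used to derive an effective number of tests or a simulation model for the next study.

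A shrinkage estimator of the joint matrix is optional; it pulls estimates toward zero. Pooling the 25 earlier tumors for the gene-gene block is also optional, and only if their RNA-seq is shown to be comparable. It would narrow the interval at 0.5 from (−0.19, 0.86) to (0.20, 0.71), but the 40-gene block would still have rank 34.

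The cost is a little analysis time, with no added patients or procedures, and fewer links will be reported as beyond chance. Re-pairing shows that an association exceeds chance, not why. Under section 3.1, patients with an outside TURBT are imaged after resection and supply FFPE tissue, so a positive result should be checked against that split.

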11.2 SAMPLE SIZE CONSIDERATIONS

The main hypothesis to be tested is whether there is association between radiogenomic features and pathologic stage. The prospective study is a pilot study to: a) generate high quality data and b) show feasibility, which we will define as know-how to create a radiogenomic workflow and to learn about the correlation structure of the radiogenomics parameters of interest, which will allow us to design future studies with adequate power. Pearson's Correlation hypothesis tests with 5% significance level (two-sided) and 80% power allows sample sizes of 10 patients to detect a difference between the null hypothesis correlation of zero and the alternative hypothesis correlation of 0.76 (23). In addition, sensitivity and specificity of several potential predictors will be estimated. The maximum width of the 95% confidence interval for proportions (sensitivities or specificities) associated with sample sizes of 10 patients are 0.63 (24). We anticipate 50% of subjects presumed to have MIBC at the time of TURBT and/or presumed not to have metastatic disease to not complete the study, i.e., undergo radical cystectomy, which will denote true pathologic stage. Thus, our final sample size to enroll is 20.

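### The plan does not fix predictors, cut-offs or a stage split in advance, so the sensitivity and specificity of anything chosen in the 10 patients will be biased upward, with no correction planned

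*Combined protocol and SAP*

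**What the plan says.** Section 11.1 applies the deconvolution algorithm to "RNA-seq data from 10 tumors in conjunction with imaging data to search for image and genomic parameters that predict tumor stage". On the number of candidates it says "we will apply 30 radiomics parameters and no more than 40 genes in our network analyses", a list limited on the basis of the group's retrospective work because many parameters in a small sample can produce false positives.

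Section 3.1 expects a "final study population of 10 MIBC who have undergone mp-4D MRI, TURBT and subsequent radical cystectomy". Section 11.2 names association of radiogenomic features with pathologic stage as the main hypothesis, and then states that "sensitivity and specificity of several potential predictors will be estimated". The precision statement is: "The maximum width of the 95% confidence interval for proportions (sensitivities or specificities) associated with sample sizes of 10 patients are 0.63".

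The statistical section does not say which predictors are meant, how cut-offs will be set, or how stage will be divided into the two groups that sensitivity and specificity require. It mentions no resampling, permutation, optimism correction or separate validation set.

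**The concern.** If a predictor or its cut-off is picked because it fits the stage of these 10 patients, its sensitivity and specificity in the same patients partly measure the picking. This differs from multiplicity in testing: adjusting a p-value leaves a biased accuracy estimate where it was. Nor does a wide confidence interval help. It describes sampling error for a predictor fixed beforehand, so after selection it is centred on the wrong value.

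At stake is how the reported accuracy is read. Section 4.0 hopes for a radio-molecular staging system more accurate than standard clinical staging. An apparent accuracy of nine or ten correct out of 10 could be taken as support for that when it is compatible with no signal at all.

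**Working it through.** **Inputs from the documents.** 10 patients (sections 3.1, 11.1, 11.2); 30 + 40 = up to 70 candidates (section 11.1); maximum 95% interval width 0.63 (section 11.2).

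**Assumptions, not in the documents.** Stage splits of 5/5, 4/6 and 3/7; continuous candidates that may predict in either direction; a cut-off chosen on the data unless noted; common correlation among candidates of 0, 0.5 or 0.8.

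**Step 1: the plan's own figure.** The exact (Clopper-Pearson) 95% interval at n = 10, maximised over the number of successes, has width 0.626, which rounds to 0.63. The figure is reproduced, for a predictor fixed in advance and a denominator of 10. Sensitivity and specificity each use only one stage group, however. The corresponding maximum widths are 0.80 for groups of 5; 0.87 and 0.76 for groups of 4 and 6; and 0.90 and 0.72 for groups of 3 and 7.

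**Step 2: chance that noise separates the groups perfectly.** With k patients in one group, one noise candidate separates perfectly in either direction with probability p = 2/C(10,k). For m independent candidates, P(at least one) = 1 − (1 − p)^m.

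| Split | p | m = 70 | m = 30 |
|---|---|---|---|
| 5/5 | 2/252 = 0.0079 | 43% | 21% |
| 4/6 | 2/210 = 0.0095 | 49% | 25% |
| 3/7 | 2/120 = 0.0167 | 69% | 40% |

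By simulation, at common correlation 0.8 with 70 candidates, this falls to 13% (5/5) and 22% (3/7).

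**Step 3: mean apparent accuracy of the best noise candidate.** Monte Carlo, 10,000 runs per setting. Each cell gives the proportion of patients correctly classified, then in brackets the mean of sensitivity and specificity, each maximised over candidates. The bracketed value for an unselected noise rule is 0.50 whatever the split.

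| Setting | 5/5 | 4/6 | 3/7 |
|---|---|---|---|
| 70, independent | 0.943 (0.943) | 0.949 (0.956) | 0.970 (0.978) |
| 70, correlation 0.5 | 0.919 (0.919) | not run | 0.944 (0.951) |
| 70, correlation 0.8 | 0.875 (0.875) | not run | 0.907 (0.905) |
| 70, independent, median cut-off | 0.886 (0.886) | 0.893 (0.910) | 0.800 (0.857) |
| 30, independent | 0.913 (0.913) | 0.920 (0.925) | 0.940 (0.948) |
| 5, independent | 0.826 (0.826) | 0.840 (0.841) | 0.868 (0.861) |
| 1 prespecified | 0.732 (0.732) | 0.746 (0.742) | 0.786 (0.759) |

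With a median cut-off and a 3/7 split, 0.80 is the highest accuracy attainable. The last row shows that choosing the cut-off alone, with no search among candidates, already produces optimism.

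**Step 4: would leave-one-out repair it?** Only poorly. With selection and cut-off repeated in each fold, 70 noise candidates give a mean Youden index (sensitivity + specificity − 1) of about −0.03, −0.10 and −0.13 for the three splits, with a standard deviation of about 0.5. When one candidate is real, separating the groups by 2 SD, the mean is still only about 0.19, 0.10 and −0.02. At n = 10 it can show that an apparent value is not validated, but it cannot estimate accuracy.

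**The case against.** The strongest reply is that the documents never say the predictors to be assessed are winners of the search. The 70-item limit is stated for the network analyses, the list comes from earlier work, and the deconvolution algorithm was developed on other tumors. The predictors and cut-offs could be fixed beforehand. This stands to the extent that the point must be conditional. It does not remove the point, because nothing in the plan commits to fixing them, and shortening the list to 70, or even 30, leaves a large search in 10 patients.

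Second, radiomic maps from one scan and genes from shared clusters are likely to be correlated, so independence is the least favourable case for the plan. That is right, and the working therefore gives a range. At correlation 0.8 the inflation is smaller but still large.

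Third, this is a feasibility pilot, the accuracy estimates are an addition to the correlation analysis, the interval width is disclosed, and no decision rule depends on them. All true, and it limits the consequence. A reader might infer that the accuracy figures are intended to size later studies, but section 11.2 ties future design to the correlation structure, not to sensitivity and specificity.

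**Conclusion.** The concern holds in conditional form. For any predictor or cut-off chosen in these 10 patients, sensitivity and specificity will be optimistic, and the 0.63 width, although arithmetically correct, does not reflect this. If every candidate were noise, the best of 70 would show mean apparent accuracy between about 0.80 and 0.97, depending on the assumed split, correlation and cut-off rule. A single prespecified noise marker with an optimised cut-off would still average about 0.73 or more.

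A reader might go further and conclude that the trial will report near-perfect accuracy whatever the truth. The documents do not support that. It requires near-independent candidates, a cut-off chosen on the data, and attention to the single best candidate, none of which the plan states. The absence of a two-group definition of stage is the more basic gap: until one exists, sensitivity and specificity are not defined.

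**What to change.** In section 11.2:

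1. Before stage is linked to the imaging and genomic data, fix the two-group split of pathologic stage and a short list of predictors. Set their cut-offs without reference to stage in these 10 patients, either from the retrospective data or by a neutral rule such as the median. Report sensitivity and specificity with exact intervals for these only, using the number of patients in each stage group as the denominator. The three cell-population proportions are not ready-made choices: section 11.1 describes them as predictors of time to recurrence, and no stage cut-offs are documented.
2. For any predictor or cut-off found in the 10 tumors, label the value apparent and exploratory. Show it against a permutation null that repeats the whole search and cut-off choice. Full enumeration is feasible, since there are only 252, 210 or 120 label assignments for splits of 5/5, 4/6 or 3/7. Do not carry the value forward as an accuracy estimate for later studies.
3. Nested leave-one-out may be shown as a check, with a statement that at n = 10 it is very imprecise and tends to fall below chance.

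The cost is a little more analysis work, some added text and less favourable reported accuracy. No new patients or data are needed.

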Next, subjects who have not had an outside TURBT will undergo TURBT in the operating room (mandatory). In pre-operative holding, a voided urine sample (50 mL) will be collected, while blood (15 mL in ACD-containing tube) and fresh frozen tumor tissue will be collected in the operating room by the BioBank staff. The results of the evaluation of the TURBT will determine if the subject has bladder cancer and if so the histology, clinical stage and grade will be noted. If the subject is found not to have MIBC, then he/she would be off study. For the subjects who had an outside TURBT, tumor material from the TURBT will be requested from the local hospital/pathology, specifically, 1 H&E slide and 10 unstained slides will be requested.

However if the subject is found to have MIBC and is deemed to be a candidate for definitive therapy by radical cystectomy without neoadjuvant chemotherapy or immunotherapy, then he/she will be scheduled for radical cystectomy within 4 weeks. At the time of radical cystectomy, additional voided urine (approximately 50 mL) will be collected in pre-operative holding and blood (15 mL in ACD-containing tube) and fresh frozen tumor tissue will be

collected in the operating room by the Biobank staff. The results of the histological evaluation of the cystectomy specimen will be reported noting histological type of bladder cancer, pathologic stage and grade.

Correlative studies

Embedded within will be crucial correlative studies that will begin to shed light on MIBC in hopes of identifying a radio-molecular staging system, which is more accurate than the standard clinical staging.

These studies will involve analyses of:

(1) Peripheral blood specimen:

An additional specimen of blood will be obtained beyond what is needed for clinical care. The amount of blood will be approximately 15 ml of extra blood collected from a vein into ACD-containing tubes. In the BioBank, the blood will be separated by centrifugation into the plasma fraction and the blood cell fractions. The fractions will be divided into aliquots for measurements which will be done either at the time of the blood sample acquisition or at a designated time later on stored specimens. Storage will be at -80^0 C in a secure biorepository freezer in CSMC BioBank.

(2) Biofluid Specimens (Urine):

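### The 0.63 maximum 95% CI width needs all 10 patients in one denominator; sensitivity and specificity split those 10, so by the exact method (inferred) neither maximum is below 0.65 and the wider is at least 0.80

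*Combined protocol and SAP*

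**What the plan says.** Section 11.2 (Sample Size Considerations) says: "In addition, sensitivity and specificity of several potential predictors will be estimated". It then gives the only precision figure for these measures: "The maximum width of the 95% confidence interval for proportions (sensitivities or specificities) associated with sample sizes of 10 patients are 0.63". It cites a textbook on rates and proportions (reference 24) but names no interval method and no target condition.

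The number analysed is 10 throughout:

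- Section 3.1 plans for a "final study population of 10 MIBC who have undergone mp-4D MRI, TURBT and subsequent radical cystectomy".
- Section 11.1 will "apply this deconvolution algorithm to the RNA-seq data from 10 tumors in conjunction with imaging data".
- Section 11.2 enrols 20 and expects half not to complete.

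Two further statements bear on who can be counted. Section 11.2 relies on completers to "undergo radical cystectomy, which will denote true pathologic stage", and Section 4.0 says: "If the subject is found not to have MIBC, then he/she would be off study". On what is to be predicted, Section 11.1 lists several targets; the search is for parameters that "predict tumor stage, outcomes and the presence of each of the cancer cell types".

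**The concern.** Sensitivity is a proportion among patients who have the target condition, and specificity a proportion among those who do not. The two denominators add up to the analysed cohort. A figure worked out with all 10 patients in the denominator therefore cannot be the maximum width for both measures when both come from the same 10.

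A reader will take 0.63 as the worst case for either measure. The pilot is meant to inform the design of later, adequately powered studies, and this is its only statement of how precisely diagnostic accuracy will be known. The stated precision is better than the design can guarantee.

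**Working it through.** **Inputs.** Stated maximum width 0.63, at 95% confidence and 10 patients (Section 11.2). Analysed cohort 10 (Sections 3.1, 11.1 and 11.2; 20 × (1 − 0.5) = 10). Both sensitivity and specificity are to be estimated (Section 11.2). The split of the 10 by target condition is not given, so every split is shown.

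**Step 1: reproduce 0.63.** For x successes in n, the exact 95% interval runs from the 0.025 quantile of Beta(x, n − x + 1) to the 0.975 quantile of Beta(x + 1, n − x), with lower limit 0 at x = 0 and upper limit 1 at x = n. At n = 10 the width is largest at x = 5: 0.8129 − 0.1871 = 0.6258, which rounds to 0.63.

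Maximum widths at n = 10 by other methods: Wald 0.620, continuity-corrected Wald 0.720, Wilson 0.527, continuity-corrected score 0.597, Agresti-Coull 0.527, Jeffreys 0.553. Of these seven methods only the exact one rounds to 0.63. A Wald interval with multiplier 2 in place of 1.96 also does: 4 × √(0.25/10) = 0.632.

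**Step 2: divide the 10 patients.** Let n1 have the target condition and n0 not, with n1 + n0 = 10. If both measures can be estimated, both groups hold at least one patient, so the larger has at most 9 and the smaller at most 5. Exact widths are:

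| Split (larger/smaller) | Maximum width, larger group | Maximum width, smaller group | Narrowest possible width, smaller group |
|---|---|---|---|
| 5/5 | 0.801 | 0.801 | 0.522 |
| 6/4 | 0.764 | 0.865 | 0.602 |
| 7/3 | 0.717 | 0.897 | 0.708 |
| 8/2 | 0.686 | 0.975 | 0.842 |
| 9/1 | 0.651 | 0.975 | 0.975 |

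The narrowest width occurs when all n are classified correctly (or all wrongly) and equals 1 − 0.025^(1/n). For n = 3 this is 1 − 0.292 = 0.708.

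**Step 3: read off the bounds.** The larger group's maximum is never below 0.651, and the smaller group's never below 0.8006. Both exceed 0.63 at every split, with no assumption about prevalence.

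**Step 4: maxima against realised widths.** These are worst cases. A realised interval can be narrower than 0.63: 0.52 for 5 of 5 correct, 0.34 for 9 of 9. In a group of 3 or fewer, however, every possible exact interval is wider than 0.63.

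**Step 5: dependence on method.** At n = 9 the maxima are exact 0.651, Wald 0.649, continuity-corrected Wald 0.760, continuity-corrected score 0.620, Jeffreys 0.573, Wilson 0.545 and Agresti-Coull 0.545. The bounds in Step 3 are therefore specific to the exact method. The direction is not: within each of the seven, the maximum at every n from 2 to 9 exceeds that method's own maximum at n = 10. At n = 1 the Wald interval is degenerate, with width 0. The multiplier-2 version also widens, to 4 × √((4/9)(5/9)/9) = 0.66 at n = 9 and 4 × √(0.24/5) = 0.88 at n = 5.

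**The case against.** **The figure is not miscalculated.** It is correct for a proportion with denominator 10, and the sentence ties it to that number of patients. This stands as far as it goes. The fault is in applying the figure to sensitivity and specificity, which the sentence does by name.

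**The method is inferred, and the inference is not unique.** This also stands. The multiplier-2 Wald interval gives 0.63 as well, and the textbook cited beside the figure cannot be consulted here. The exact table should go in only if the authors confirm that method.

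**The bounds need both groups to be non-empty.** True. If the target were muscle invasion at TURBT, all 10 analysed patients would have it. Sensitivity would keep its maximum of 0.63, but specificity could not be estimated at all, which contradicts the stated aim of estimating both.

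**Perhaps 10 per class was meant, or more than 10 patients could contribute.** Ten per class needs 20 evaluable patients, and the plan provides 10. All 20 are imaged, and stage is reported on the TURBT specimen too, so an imaging-only predictor judged against TURBT stage could in principle use more patients. But subjects without MIBC leave the study, true stage is defined by cystectomy, and Section 11.1 analyses 10 tumors. This is a caveat and does not rescue the figure.

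**Little depends on it.** Agreed. The objective is feasibility and correlation structure, and a width of 0.63 already signals poor precision.

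**Conclusion.** The concern holds, as a minor one. The 0.63 is right for one proportion based on all 10 patients but is not the maximum width for sensitivity or specificity once those 10 are divided. By the exact method the two maxima are at least 0.65 each and the wider is at least 0.80, rising to 0.975 at the most uneven splits.

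This rests on three conditions: the analysed cohort is 10, as the plan says in three places; both measures can be estimated, so neither group is empty; and the interval is the exact one, which is inferred. Under another method the figures change, but the widening on division remains for groups of 2 to 9 in all those tried. No decision rule, enrolment figure or design feature depends on 0.63.

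**What to change.** Replace the sentence on interval width in Section 11.2 with wording such as:

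> A proportion based on all 10 patients has an exact (Clopper-Pearson) 95% interval no wider than 0.63. Sensitivity and specificity each use only some of the 10, so their largest possible widths are greater and depend on how the target condition divides the patients: 0.801 for both at 5/5, 0.764 and 0.865 at 6/4, 0.717 and 0.897 at 7/3, 0.686 and 0.975 at 8/2, 0.651 and 0.975 at 9/1.

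If the authors used another method, they should name it and recompute the widths by it. If they prefer not to list splits, the minimum is to limit 0.63 to a denominator of 10 and say that sensitivity and specificity will have smaller denominators and wider maximum intervals. The choice of target condition or conditions is theirs.

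The cost is one sentence becoming two and a less favourable statement of precision. Enrolment of 20 and the design do not change.
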